culprit lesions.²² The combination of stenosis + atheroma burden + luminal area produced an odds ratio of 3.99 (95% CI: 1.74-9.13, p=0.001) for culprit plaque. The GLAGOV study showed that PCKS9 inhibition reduced the percent atheroma volume of coronary arteries over a 78 week treatment period.²³ With atheroma volume now established as a viable biomarker, vwMRI is the optimal test to monitor it and stenosis, both for ICAD and in other locations of the cerebrovasculature, such as the carotid arteries, cervical vertebral arteries, and aortic arch.

A.5. Impact

The result of this study will be a dataset that lays the foundation for a randomized controlled trial of Repatha in ICAD patients. The data collected in this study will allow us to optimize a future clinical trial designed to demonstrate a reduction in stroke risk, ultimately making more efficient and economical progress towards our ultimate research goal of preventing stroke with Repatha. While we are proposing future studies to reduce ICAD stroke risk, it should be noted that our study will also evaluate the potential for Repatha to decrease cerebrovasculature stenosis and plaque burden, which would be a compelling primary prevention indication.

B. Approach

B.1. Study Hypothesis

We hypothesize that inhibition of PCSK9 with Repatha in patients with moderate to severe intracranial atherosclerosis will reduce validated biomarkers of stroke risk (stenosis and percent atheroma volume). To answer our hypothesis, we propose a single arm study of Repatha in 150 patients with a prior history of ischemic stroke and ICAD causing at least 50% stenosis of a major intracranial artery in the Circle of Willis ("index artery").

B.2. Study Design

We will enroll 150 ICAD patients with a prior history of ischemic stroke. Patients will be enrolled at up to 8 medical centers in North America. All patients will receive Repatha for 78 weeks and will have an MRI before beginning study medication and a comparison MRI immediately after completing study medication.

B.3. Investigational Treatment

The investigational treatment is Repatha 140 mg administered subcutaneously with a single-dose pre-filled pen syringe every 2 weeks for a total of 39 treatments. Dose modification is not allowed.

B.3.a. Inclusion Criteria

- Adult patients, ≥ 18 years of age

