
C.2.a. Secondary endpoint 1 measurement:

a) ICAD post-contrast plaque enhancement (PPE): is a dichotomous variable evaluated on the T1 pre- and post-gadolinium sequences, with multiplanar reconstruction so the ICAD can be seen in cross section.²⁶ PPE is defined by placing a region-of-interest over areas of gadolinium enhancement in ICAD to evaluate if it is equal to or exceeds the signal intensity of the pituitary infundibulum, as previously described.²⁷

- b) Carotid intraplaque hemorrhage (IPH): MPRAGE positive plaque is defined as voxels with at least 2-fold signal intensity compared to sternocleidomastoid muscle as previously described. MPRAGE positive plaques can be reliably identified. Kappa values for inter- and intra-rater reliability for detection of MPRAGE positive plaque were 0.806 and 0.818 respectively (very good agreement).^{28,29}
- c) MRA Flow Dynamics (**MFD**): We will measure MFD using accepted quantitative MRA methodology. The VERiTAS study provided prospective confirmation of the importance of MFD as a biomarker of stroke risk for patients with ICAD. Given that MFD can easily be measured in our vwMRI protocol, we will acquire the data required for its quantification.

C.3. Secondary endpoint 2

To better understand the mechanism of Repatha's effect on intra- and extracranial atherosclerosis, we will measure the endpoint of change in cholesterol markers [LDL-C, HDL-C, lipoprotein (a), apolipoprotein B, and triglyceride level]. The change in cholesterol markers will be correlated with the primary and secondary study endpoints on vwMRI. Cholesterol values will be measured at the baseline and comparison MRIs, which are 78 weeks apart. If standard of care lab values are available within 30 days of the study visit, they can be used in place of the study lab value. An additional exploratory outcome that we will measure is the composite endpoint of "recurrent stroke," which encompasses new patient-reported symptomatic ischemic stroke, transient ischemic attack, or asymptomatic strokes that emerge between MRIs.

C.3.a. Secondary endpoint 2 measurement:

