We will fit a mixed effects linear regression model, specifically a LOESS smoothing curve, to change in stenosis/PAV and on-treatment LDL-C, HDL-C, and lipoprotein(a). We will also use a multivariable linear regression model with the outcome of the primary endpoints, adjusted for covariates that could be confounders such as age, gender, smoking, statin use/dose and relevant medical comorbidities. The primary endpoints will also be compared to an assumed value of 0% change in stenosis and PAV that would correspond to optimal medical management without a PCSK9 inhibitor. Although, some studies have suggested statin therapy can reduce carotid atherosclerosis, no such effect is known for ICAD. For this analysis, we will use linear mixed effects model to detect differences in the stenosis and PAV endpoints between patients taking Repatha or the presumed historical control values of 0% change. For the secondary endpoints, we will use logistic and linear regression depending on the nature of the variable and use the primary predictors of on-treatment LDL-C, HDL-C, and lipoprotein(a). For the exploratory endpoint of recurrent stroke, we will use the above mentioned methods as well as a Cox proportional hazards model for the endpoint of recurrent stroke with the observed rate in this study compared to controls matched according to degree to stenosis of the index artery. Due to differences in arterial structure and flow dynamics, there may be a more significant plaque reduction in certain intracranial vessels. We anticipate subgroup analyses, for example comparing change in stenosis or PAV in the middle cerebral artery versus the vertebral artery.

D.2. Power Analysis

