We power our study on the primary endpoint of change in stenosis and PAV. The GLAGOV trial showed 0.95% reduction in PAV for patients randomized to Repatha versus a 0.05% increase in PAV for patients in the placebo arm and was 78 weeks in length. Because the major intracranial arteries have a similar luminal diameter to coronary arteries, we may reasonably expect a 1% reduction in PAV for our 78 week study as documented in previous literature. Patients with intracranial atherosclerosis can be expected to have at least 3 additional sites of atherosclerosis, including extracranial arteries, that will be included in the series of PAV outcomes. Each subject will provide four sites of atherosclerosis and therefore, 4 PAV measurements. This cluster designed study will be modeled by a mixed effects linear regression to account for the cluster of arteries per patient. We obtain >80% power for our sample size of 150 patients, two-sided significance level 0.05, and a conservative assumed standard deviation of 4% from previous studies for the assumed 1% reduction in PAV against the documented control PAV of 0%.²³ With 150 patients, the minimum effect size possible to detect with 80% power is a 0.51% reduction. A 0.50% difference has been reported to be the cutoff to distinguish individuals that experience cardiovascular events versus those who do not.²³ Assuming a withdrawal rate of 25-30%, we would still reach >90% power for a 1% reduction with the above-listed conditions. We do not expect to show a significant reduction in recurrent stroke, but anticipate seeing a trend towards that outcome. This data could be used to accurately construct and power a subsequent trial with the primary outcome of recurrent stroke. Finally, in GLAGOV the linear relationship between change in stenosis, PAV and on-treatment LDL-C was very robust. We will be replicate this finding through means of a generalized linear mixed effects model. Our effective sample size may be sufficiently large enough to match the GLAGOV trial as each patient will be able to contribute an average of 4 arteries giving us an expected sample size between 800 and 1200 dependent on a conservative prediction of intra-class correlation. All reported p-values will be twosided and deemed significant at the 0.05 level.

D.3. Loss to Follow-up

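### The Cox comparison of recurrent stroke with stenosis-matched controls cannot be interpreted as written: no control source is named, and the composite includes silent infarcts that have no event time

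*Combined protocol and SAP*

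**What the plan says.** **Design.** B.1 states "we propose a single arm study of Repatha in 150 patients", and B.2 adds "All patients will receive Repatha for 78 weeks". No concurrent comparison group is enrolled.

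**Endpoint.** C.3 defines recurrent stroke, an exploratory outcome, as a composite of "new patient-reported symptomatic ischemic stroke, transient ischemic attack, or asymptomatic strokes that emerge between MRIs".

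**Analysis.** D.1 says "For the exploratory endpoint of recurrent stroke, we will use the above mentioned methods" and then adds a "Cox proportional hazards model for the endpoint of recurrent stroke with the observed rate in this study compared to controls matched". The only matching factor is the degree of stenosis of the index artery. D.1 gives no source, calendar period, number, eligibility, event definition or imaging schedule for these controls. The other control in D.1, an assumed 0% change in stenosis and PAV, is an imaging value and supplies no stroke events.

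**Timing.** B.9 schedules vessel wall MRI at Day 1 and Day 546 only. Stroke adjudication is scheduled at seven contacts from Day 60 to Day 546.

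**Missing scans.** D.3 anticipates that up to 25-30% will not complete the follow-up visit or the second MRI.

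**Use.** D.2 expects no significant reduction in recurrent stroke but anticipates a trend, and says: "This data could be used to accurately construct and power a subsequent trial with the primary outcome of recurrent stroke".

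**The concern.** A Cox comparison needs individual event times in both groups and the same events counted in both. The plan secures neither.

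A silent infarct is known only to have arisen somewhere in a 78-week interval. No rule dates it, and no interval-censored method is named. Patients without a second scan cannot contribute one, and no rule covers them. If the external controls were followed clinically, without paired MRIs, silent events would count on the treated side only. Matching on stenosis alone is also thin for a non-randomised comparison: D.1 names age, gender, smoking, statin use or dose and comorbidities as possible confounders of the primary endpoints, but does not clearly carry them over to this model.

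What is at stake is the reading of the stroke result. A trend towards reduction needs a comparator, and this is the only stroke comparison in the plan. A distorted hazard ratio could hide a benefit, or make it look like harm, when the next trial is being planned.

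**Working it through.** The plan gives no stroke event rate, hazard ratio, control number or power, so there is no figure of its own to reproduce. The risks below are assumptions; only the missing-scan range and the scan days come from the documents.

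**Inputs**
- Symptomatic risk over 78 weeks: 8% in both groups, so no true difference (assumed).
- Silent infarct in patients without a symptomatic event, as a share of all patients: 5% to 10% (assumed).
- Second MRI missing: 25% to 30% (D.3, which gives this as an upper range for missing the visit or the scan).
- Controls: no paired MRIs, so no silent events counted (assumed; the plan does not say).

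**Step 1: silent infarcts actually seen**, if missing scans are unrelated to risk
- 5% true: 5 × 0.70 = 3.5% to 5 × 0.75 = 3.75%.
- 10% true: 10 × 0.70 = 7.0% to 10 × 0.75 = 7.5%.

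Counting patients without a second scan as free of silent infarct therefore understates that component by 25-30%.

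**Step 2: apparent hazard ratio**, as a ratio of cumulative hazards, ln(1 − treated risk) / ln(1 − control risk), with ln(0.92) = −0.0834

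| Silent, true | Scans missing | Treated risk | Apparent HR |
|---|---|---|---|
| 5% | 30% | 11.5% | 0.1222/0.0834 = 1.47 |
| 5% | 25% | 11.75% | 0.1250/0.0834 = 1.50 |
| 10% | 30% | 15.0% | 0.1625/0.0834 = 1.95 |
| 10% | 25% | 15.5% | 0.1684/0.0834 = 2.02 |

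The result is about 1.5 to 2.0 with no true effect. If every patient had the second scan, the bias would be larger: ln(0.87)/ln(0.92) = 1.67 and ln(0.82)/ln(0.92) = 2.38.

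**Step 3: does an actual Cox fit behave this way?** The ratio in step 2 is not a Cox estimate with tied events at the last scan. A simulation therefore fitted a Cox model (Efron ties, 8,000 per group, 546 days, 27.5% missing second scans), dating silent infarcts to Day 546. Assumed risks were 10-20% symptomatic and 5-20% silent.

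| Controls | True HR 1.0 estimated as | True HR 0.70 estimated as |
|---|---|---|
| No paired MRI | 1.08 to 2.33 | 0.82 to 1.85 |
| Same two scans, same missingness | 0.98 to 1.06 | 0.65 to 0.73 |

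The bias comes from unequal ascertainment. With the same MRI schedule in both groups, dating silent infarcts to the last scan left the hazard ratio essentially unbiased, within simulation noise.

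**The case against.** Four points on the other side have force.

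1. **External controls are legitimate.** A reader might infer that a single-arm study cannot have controls with event times, so the analysis is impossible. The documents do not support that. Matched controls can come from an outside patient-level source, and the text does not say that none exists. The document's opening part was not available for this review, so a source named there cannot be excluded. What stands is that D.1 specifies none.

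2. **Missing event times are not fatal alone.** A reader might infer that undated silent infarcts make any Cox result invalid. Step 3 shows otherwise when both groups share the scan schedule. Symptomatic events can be dated from the seven scheduled contacts. The methods carried over in D.1 also include logistic regression, which needs no event time. Even so, D.1 applies the Cox model to the whole composite without separating the parts.

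3. **The use in planning is conditional.** A reader might infer that D.2 commits the hazard ratio to powering the next trial. It says only that the data could be used, and the within-study event rate remains useful for that without any control comparison. That D.2 also anticipates a trend is what gives the comparison weight.

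4. **The endpoint is exploratory**, and no significant result is expected. This limits the consequence but does not make the estimate readable.

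**Conclusion.** The concern holds in a limited form. As written, the stroke comparison cannot be interpreted, because the controls' source, period and imaging are undefined, matching rests on stenosis alone, and the composite mixes dated events with infarcts found only at the final scan.

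It is biased against the drug if the controls lack paired MRIs. Under the assumed risks (8% symptomatic in both groups, 5-10% silent) and 25-30% missing second scans, a null effect would appear as a hazard ratio of about 1.5 to 2.0. Other assumed risks in the simulation gave 1.08 to 2.33, so the size depends on inputs that the documents do not give. With controls on the same MRI schedule, this bias largely disappears; incomplete control of confounding would remain. Calling the analysis invalid without qualification would go too far.

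The change should be made: the endpoint is exploratory, but a better analysis uses data already collected.

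**What to change.** Revise D.1 as follows.

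- Analyse dated symptomatic ischemic stroke by Kaplan-Meier or person-time rate with a 95% confidence interval, and TIA separately in the same way.
- Report new silent infarcts as a proportion with an exact 95% confidence interval among patients with both MRIs, and state how many lack the second scan. Do not count those patients as event-free.
- Exclude silent infarcts from any Cox model.
- Either drop the comparison with controls, or label it descriptive, limit it to symptomatic events, and adjust for the confounders D.1 already lists. If it is kept, name the source, period, eligibility and event definition of the controls, and confirm that patient-level event times are available.

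The cost is SAP wording; no new data are needed from study patients. The downside is fewer events in the time-to-event analysis and no formal hazard ratio for the composite.

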Based on the SPRINT MIND trial, we anticipate that up to 25-30% will not complete the follow-up clinic visit or vwMRI, and have accounted for this in our sample size calculation.³¹ If less patients than expected return for yearly follow-up MRI scans, we can enroll additional patients as needed, but do not expect this to be necessary or costly if necessary. If we have difficulty finding enough patients to enroll in the study, we will expand enrollment to the VA hospitals at our study sites, which would significantly increase potential patients.

E. Safety Definitions, Reporting, and Monitoring

E.1. Adverse Event (AE)

An AE is any untoward medical occurrence in a patient administered the study drug which may or may not have a causal relationship with the study drug. Therefore, an AE is any unfavorable and

unintended sign (including abnormal laboratory finding), symptom, or disease which is temporally associated with the use of a study drug, whether or not considered related to the study drug. An AE also includes any worsening (i.e. any clinically significant change in frequency and/or intensity) of a pre-existing condition that is temporally associated with the use of the study drug. The most commonly occurring adverse reactions reported from clinical studies with Repatha were injection site reactions (including erythema/redness, itching, swelling, pain, tenderness), upper respiratory tract signs and symptoms (mainly nasopharyngitis, sinusitis, influenza, and upper respiratory tract infection), back pain, urinary tract infection, and cough. For this study, investigators will record all potential AEs, but the following are always considered as AEs:

- a) Increase in ALT: ALT >3 x ULN
- b) Allergic events: allergic drug reactions and/or local injection site reactions deemed to be allergic by the Investigator (or have an allergic component), that require consultation with another physician for further evaluation of hypersensitivity/allergy as per the Investigator's medical judgment should be reported as an AE.

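### D.2's 0.51% minimum detectable PAV reduction holds only if all 150 patients have the week-78 scan; at the plan's own 25–30% loss it is about 0.59–0.61%

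*Combined protocol and SAP*

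**What the plan says.** D.2 (Power Analysis) sets up a one-sample comparison of PAV change with zero:

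- Size and significance level: "We obtain >80% power for our sample size of 150 patients, two-sided significance level 0.05".
- Spread: a "conservative assumed standard deviation of 4% from previous studies".
- Effect: "for the assumed 1% reduction in PAV against the documented control PAV of 0"%.
- Clustering: "Each subject will provide four sites of atherosclerosis and therefore, 4 PAV measurements".
- ICC: mentioned only in a later sentence about the effective sample size, described as "dependent on a conservative prediction of intra-class correlation". No value is given.

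D.2 then states the sensitivity figure: "With 150 patients, the minimum effect size possible to detect with 80% power is a 0.51% reduction". The next sentence gives a benchmark: "A 0.50% difference has been reported to be the cutoff to distinguish individuals that experience cardiovascular events versus those who do not". Only after that does D.2 bring in a 25–30% withdrawal rate, and it does so only to claim more than 90% power for the 1% reduction.

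D.3 (Loss to Follow-up) puts the share of patients who will miss the follow-up visit or scan at up to 25–30%, "and have accounted for this in our sample size calculation". B.7 lets the investigator replace withdrawn patients. D.3 allows extra enrolment if fewer patients return than expected, and adds that this is not expected to be needed.

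**The concern.** The primary endpoints in C.1 are changes from baseline to week 78, and the schedule in B.9 has two vessel wall MRIs, on Day 1 and Day 546. A patient without the second scan has no observed change, and there is no intermediate scan for a mixed model to use. The relevant number for any detectable-effect statement is therefore the number of completers, not the number enrolled.

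D.2 uses completers for the 1% effect but enrolled patients for the 0.51% figure, and a reader of D.3 would assume that both allow for loss. The 0.51% figure also stands beside a 0.50% cut-off linked to clinical events, so it reads as a statement that the study has about 80% power for a change of that size. This is the plan's only sensitivity statement below its 1% assumption, and that assumption is carried over from coronary arteries. If the true effect is smaller than 1%, someone planning the randomised trial that this study is meant to inform could overestimate what a non-significant result rules out.

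**Working it through.** **Inputs.** From D.2: 150 patients, 4 sites each, SD 4%, two-sided 0.05, 80% power, reference value 0%. From D.2 and D.3: loss of 25–30%, which leaves 150 × 0.75 = 112.5 (taken as 112) or 150 × 0.70 = 105 completers. The ICC is not given, so it is an assumption here. The 800 to 1200 effective sample size in D.2 cannot supply it, because 150 × 4 is only 600.

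**Formulas** (normal approximation, n completers):

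- Neff = 4n / (1 + 3 × ICC)
- Minimum detectable effect (MDE) = (1.960 + 0.842) × 4 / √Neff = 11.208 / √Neff
- Power for a true reduction d = Φ(d × √Neff / 4 − 1.960)

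**The plan's 0.51%.** Without an ICC it has no unique reproduction. With 150 completers, the MDE is 0.457% at ICC 0 and 0.915% at ICC 1. Solving for 0.51%:

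- Neff = (11.208 / 0.51)² ≈ 483
- design effect = 600 / 483 ≈ 1.243
- ICC = 0.243 / 3 ≈ 0.081 (0.073 to 0.089 if 0.51 is a rounding of 0.505 to 0.515)

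The only other match found is ICC 0 with 20% loss (480 measurements, 0.511%), and 20% is not a loss rate in the plan.

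**Could 0.51% already allow for the stated loss?** No. After 25–30% loss there are 420–450 measurements (105 × 4 to 112.5 × 4), fewer than the 483 effective observations needed. The design effect would have to be 0.87 to 0.93, which means a negative ICC of about −0.04 to −0.02.

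**After loss, at the implied ICC:**

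- 112 completers: Neff = 448 / 1.243 ≈ 360; MDE = 11.208 / √360 ≈ 0.59%; power for 0.50% = Φ(2.372 − 1.960) ≈ 66%.
- 105 completers: Neff = 420 / 1.243 ≈ 338; MDE = 11.208 / √338 ≈ 0.61%; power for 0.50% = Φ(2.298 − 1.960) ≈ 63%.
- For comparison, 150 completers: power for 0.50% = Φ(2.747 − 1.960) ≈ 78%.

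Direct rescaling agrees: 0.51 × √(150/112) = 0.590 and 0.51 × √(150/105) = 0.610.

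**Sensitivity to the ICC:**

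| ICC | Completers | MDE | Power for 0.50% | Power for 1% |
|---|---|---|---|---|
| 0 | 112 | 0.53% | 75% | >99% |
| 0 | 105 | 0.55% | 73% | >99% |
| 0.081 | 112 | 0.59% | 66% | 99.7% |
| 0.081 | 105 | 0.61% | 63% | 99.6% |
| 0.3 | 112 | 0.73% | 48% | 97% |
| 0.3 | 105 | 0.75% | 46% | 96% |

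The claim of more than 90% power for 1% after loss is thus confirmed at the implied ICC. It would come down to about 90% only at ICC 0.5 with 30% loss.

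**The case against.** The sentence about 0.51% is explicitly conditional on 150 patients, and on those terms it is not a miscalculation. The study is powered on a 1% reduction, the loss is applied to that effect, and the result is right, so D.3's statement is true of the effect that drives the design. D.3 gives the loss as an upper bound, so 0.59–0.61% is the unfavourable end. The new figures depend on a back-solved ICC. The 0.50% cut-off is mentioned once, as a difference between individuals with and without events, and nowhere is it made a target or a decision rule. All of this stands. It limits the point to a sensitivity figure that is incompletely reported.

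Replacement and extra enrolment are a weaker defence. Both are discretionary, and neither sets a number of completers to reach. D.3's trigger is a lower return than expected, and 25–30% loss is what it already anticipates. Keeping 0.51% at that loss would need 150 / 0.75 = 200 to 150 / 0.70 ≈ 215 patients enrolled. If restoring 150 completers is the intention, the figure stands, but the plan does not say so.

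A reader might also infer that dropout is what puts 0.50% beyond the study, or that a 0.50% change cannot be detected at all. Neither follows. At 0.51% the benchmark is already narrowly missed with no loss, and loss only widens the gap. An MDE at 80% power is not a detection limit: after loss, an observed reduction of 1.960 × 4 / √360 ≈ 0.41% to 1.960 × 4 / √338 ≈ 0.43% would still be significant.

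**Conclusion.** The point holds for the sensitivity figure. The 0.51% requires a week-78 scan from all 150 patients. At the plan's own 25–30% loss, it becomes about 0.59–0.61%, and power for a 0.50% reduction falls from about 78% to about 63–66%. These values rest on the plan's SD of 4%, four sites per patient, and an ICC of about 0.08 inferred from the 0.51% itself. The direction does not depend on that inference: at ICC 0, the most favourable non-negative value, the figure is still 0.53–0.55%, and it is larger at any higher ICC.

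The documents do not support reading this as an underpowered trial or a wrong sample size. Power for the 1% effect that the study was designed around remains above 99% after loss at the implied ICC.

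**What to change.** In D.2:

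- State the ICC that was used.
- Beside the 150-completer figure, give the minimum detectable change for the completers left after 25–30% loss (0.59–0.61% if the ICC is 0.08).
- Say that the 0.50% cut-off falls below 80% power in both cases: slightly with 150 completers (about 78%) and materially after loss (about 63–66%).

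In D.3, limit the statement that loss is covered to the claim of more than 90% power for a 1% reduction. If replacement up to 150 completers under B.7 is intended, say so in D.2 and D.3 instead.

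The cost is a few sentences and a less favourable sensitivity figure. No patients are added, and the primary analysis does not change.

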Proprotein convertase subtilisin/kexin type 9 (PCSK9) inhibitors, by modifying LDL receptors, have been shown to dramatically lower LDL. There is robust evidence that lowering LDL cholesterol is beneficial in atherosclerotic disease, due to plaque-stabilizing effects. The FOURIER and ODYSSEY studies showed that patients randomized to PCSK9 inhibition had dramatic LDL reduction and a lower overall incidence of stroke (1.2 versus 1.6% of patients over three years). The GLAGOV study showed that, compared to placebo, evolocumab (Repatha) decreased coronary artery plaque volume. GLAGOV also demonstrated a linear relationship between LDL cholesterol reduction and plaque volume regression. However, these findings do not provide adequate evidence that Repatha reduces the risk of ICAD stroke. FOURIER and ODYSSEY did not adjudicate the etiology of stroke and, for the stroke outcome, they included cardioembolic and lacunar strokes, which typically account for up to 50% strokes. The risk reduction from a PCSK9 inhibitor like Repatha would primarily be for patients with large artery atherosclerosis, such as ICAD. As a result, the absolute risk reduction seen in those studies does not represent the potential of Repatha in a patient population at risk for stroke.

A.3. Repatha

Repatha is an FDA-approved PCSK9 inhibitor shown to reduce the risk of cardiovascular events, including myocardial infarction, stroke, and coronary revascularization. Repatha is a patient-administered subcutaneous injection that is well tolerated. Common side effects include flu-like symptoms, cough, back pain, and dizziness. Further information can be obtained at: (https://www.pi.amgen.com/~/media/amgen/repositorysites/pi-amgen-com/repatha/repatha_pi_hcp_english.pdf).

A.4. Stenosis and Plaque Atheroma Volume Measured on vwMRI

We will measure both stenosis and atheroma volume to have two primary outcomes with validated biomarker potential. Stenosis is measured using WASID criteria.¹³ Atheroma volume is either directly measured or inferred by measuring the area of entire vessel (the outer wall boundary area) on an axial slice and subtracting the lumen area. In a study of middle cerebral artery ICAD, the atheroma volume on vwMRI was larger in the 26 symptomatic patients compared to the 35 asymptomatic patients (12.9±3.1 mm² vs. 8.2±3.6 mm², p<0.001). A second study enrolled 139 patients with moderate to severe middle cerebral artery atherosclerosis, who contributed 112 culprit and 53 non-

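### D.2 rests replication of GLAGOV's LDL-C relation on an effective sample size of 800 to 1200, which 150 patients with four arteries cannot supply and which would not by itself match slope precision

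*Combined protocol and SAP*

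**What the plan says.** B.1 states the design: "we propose a single arm study of Repatha in 150 patients". B.2 adds: "All patients will receive Repatha for 78 weeks". D.1 relates change in stenosis and percent atheroma volume (PAV) to on-treatment LDL-C, and C.3 places the cholesterol correlations under secondary endpoint 2. The schedule of activities has a lipid panel at screening/baseline and at day 546 only, so each patient has one on-treatment LDL-C value.

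D.2 reports that "in GLAGOV the linear relationship between change in stenosis, PAV and on-treatment LDL-C was very robust" and says the study will replicate this with a mixed model. The support offered is that the effective sample size "may be sufficiently large enough to match the GLAGOV trial", because patients contribute four arteries on average, for an expected 800 to 1200 depending on the intra-class correlation (ICC). D.2 describes GLAGOV as a two-arm comparison: "0.95% reduction in PAV for patients randomized to Repatha versus a 0.05% increase in PAV for patients in the placebo arm". No section gives an expected slope, an on-treatment LDL-C SD, GLAGOV's sample size or a precision calculation for the slope.

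**The concern.** There are two problems. The first is internal to D.2: the count offered as comparable with GLAGOV exceeds the number of artery-level changes that the design can produce, and it disagrees with the detectable effect quoted in the same section.

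The second is that a count is not enough for a regression slope. The spread of the predictor matters as much. A trial with treated and placebo patients has LDL-C values from both groups; this one has treated patients only. Additional arteries add outcome measurements but no LDL-C spread, because all arteries of a patient share one LDL-C value. The historical control of 0% change in D.1 brings no LDL-C values with it.

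At stake is how the LDL-C analysis will be read. A.5 presents the dataset as the basis for a later randomized trial, and D.2 judges all p-values at 0.05. If replication is announced on the strength of a sample said to match GLAGOV, an imprecise slope could be mistaken for evidence against the relation.

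**Working it through.** **Inputs from D.2 and D.3:** 150 patients; 4 arteries each; SD of PAV change 4%; two-sided 5% level; detectable effect 0.51% at 80% power; loss 25 to 30%; claimed effective sample size 800 to 1200.

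**Step 1: the claimed count.** With N patients and m arteries each, n_eff = N·m / (1 + (m − 1)·ICC).

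- Ceiling at ICC 0: 150 × 4 = 600. After loss: 600 × 0.75 = 450 and 600 × 0.70 = 420.
- At ICC 0.1, 0.3, 0.5 and 1, n_eff is 462, 316, 240 and 150 before loss.
- ICC needed for 800: (600/800 − 1)/3 = −0.083. For 1200: (600/1200 − 1)/3 = −0.167.
- At ICC 0, reaching 800 or 1200 needs 5.3 or 8 arteries per patient, or 200 or 300 patients with four arteries.
- Counting baseline and follow-up scans separately gives 600 × 2 = 1200 (840 to 900 after loss), but each change uses both scans, so this is not a count of changes.

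The 800 to 1200 figure does not reproduce.

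**Step 2: D.2's own detectable effect.** With MDE = (1.96 + 0.84) × 4 / √n_eff, setting MDE = 0.51 gives n_eff = 483. The design effect is 600/483 = 1.24 and the ICC about 0.08. After 30 to 25% loss this leaves 338 to 362. An n_eff of 800 or 1200 would have given an MDE of 0.40 or 0.32.

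**Step 3: precision of the slope.** SE(slope) = σ / (SD_LDL × √n_eff).

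Assumptions, none fixed by the documents: GLAGOV's relation was fitted across two equal arms; mean LDL-C differs between them by d within-arm SDs; within-arm LDL-C SD and residual SD σ are the same in both trials. Pooled LDL-C variance is then 1 + d²/4 times the within-arm variance.

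| d | Variance ratio | SE ratio, single arm to two arms, equal n | Two-arm equivalent of 338 to 362 |
|---|---|---|---|
| 1 | 1.25 | 1.12 | 270 to 290 |
| 2 | 2.00 | 1.41 | 169 to 181 |
| 3 | 3.25 | 1.80 | 104 to 111 |
| 4 | 5.00 | 2.24 | 68 to 72 |

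A simulation with 800 observations per sample gave variance ratios of 1.21, 2.00 and 3.38 at d = 1, 2 and 3. If only treated patients were fitted in GLAGOV, d = 0 and the ratio is 1.

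**Step 4: what this does to significance.** Two illustrations at n_eff = 338:

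- *Slope scaled to the PAV contrast.* Take the arm difference in D.2, 0.95 + 0.05 = 1.00% PAV, as the effect of the whole between-arm LDL-C gap. Single-arm power is Φ((1/d) × √338 / 4 − 1.96): 63% at d = 2 and 33% at d = 3. The two-arm values are 90% and 79%.
- *Slope scaled to a correlation.* Assume a two-arm correlation of 0.30. Dividing r²/(1 − r²) by the variance ratio gives 0.22, 0.17 and 0.14 at d = 2, 3 and 4, with Fisher-z power of about 98%, 88% and 73%.

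The illustrations disagree because the documents fix neither the slope nor the LDL-C spread.

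**The case against.** The claim in D.2 is hedged, and the study is powered on mean change in stenosis and PAV, not on this relation. That limits the weight of the point. The hedge covers whether the sample matches GLAGOV; it does not make 800 to 1200 attainable.

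Patients may have more than four qualifying arteries, and B.7 and D.3 allow replacement or extra enrolment. But D.2 itself uses an average of four, and 150 completers would still give only 600 changes.

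The documents do not say which patients entered GLAGOV's fit. A.2 and D.2 report the relation near the Repatha-placebo comparison, and A.2 says that in two other trials "patients randomized to PCSK9 inhibition had dramatic LDL reduction", so a pooled fit with a wide LDL-C gap is plausible. It remains an inference, and the objection stands to that extent.

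Equal within-arm spread is also assumed. B.3.a sets only lower limits on LDL-C and admits patients with a statin contraindication, so the spread here could be wider. A within-arm SD 1.41 times larger would cancel the whole loss at d = 2, and one 1.80 times larger the loss at d = 3. This stands too.

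Finally, a reader might infer that a flat or non-significant slope is the expected result of treating everyone. The documents do not support that. Under a linear relation, a narrower LDL-C range leaves the expected slope unchanged and only widens its interval. Non-significance is likely under some of the assumptions above and unlikely under others.

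**Conclusion.** The point holds in two parts of unequal firmness.

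The firm part needs only D.2. With four arteries per patient and a non-negative ICC, 800 to 1200 is impossible: the ceiling is 600, and the section's own detectable effect corresponds to about 483, or 338 to 362 after the planned loss.

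The conditional part is that a matching count would not by itself secure matching slope precision. The direction follows if GLAGOV's fit pooled both arms and within-arm spread is similar; the standard error is then 1.12 to 2.24 times larger at equal n for d from 1 to 4. The size cannot be fixed, and the loss is zero if the fit used treated patients only. Even then, D.2 would offer no basis for the precision of its slope.

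The single-arm design does not prevent estimation of the slope and does not bias it towards zero. What is wrong is the stated ground for expecting replication.

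**What to change.** In D.2:

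1. Delete the 800 to 1200 figure and the statement that the sample may match GLAGOV for this relation.
2. State the expected standard error or 95% confidence interval width of the LDL-C slope, calculated from the number of completers, the assumed ICC and a stated range of on-treatment LDL-C SD.
3. Report the slope per fixed LDL-C unit (for example per 10 mg/dL) with its 95% confidence interval.
4. State that a non-significant slope alone will not be read as failure to replicate.

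The cost is one extra calculation, some SAP wording and a less favourable stated claim. Enrolment, visits and imaging are unaffected.
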